5.4 PARTICIPANT WITHDRAWAL OR TERMINATION

5.4.1 REASONS FOR WITHDRAWAL OR TERMINATION

Arm 1: Phase 1B

The PI will terminate a Phase IB participant if they experience a DLT, more than one IT, or begin a contradictory medication during the course of the trial. Patients may withdraw from the trial at any time upon request. Any withdrawn participants from Phase IB will be replaced to maintain 3 patient cohorts. Their reason for withdrawal will be noted.

Arm 2: Phase 2

The PI will terminate a Phase II study participant if they present with any clinical adverse event (AE) or other medical complication such that continued participation in the study would not be in the best interest of the participant. The PI will terminate a participant if they miss more than 2 doses of topical Verapamil in a week. Compliance will be checked using a patient dosing diary. Participants may withdraw from the trial at any time upon request. Any withdrawn participant will be replaced with a new enrollment.

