5.4.2 HANDLING OF PARTICIPANT WITHDRAWALS OR TERMINATION

Patients that withdraw or are terminated from either arm of the study due to an adverse event will be followed for up to 1 year to monitor for additional safety data.

Phase 1B: Any withdrawn participants will be replaced to maintain 3 patient cohorts.. Their reason for withdrawal will be noted.

Phase 2: Any withdrawn participant will be replaced with a new enrollment.

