7.3.5 EARLY TERMINATION VISIT

In the event of an early termination participants will be asked to perform all the procedures for the final visit (Phase 1B and 2) at their final visit.

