10 STATISTICAL CONSIDERATIONS

10.1 STATISTICAL AND ANALYTICAL PLANS

All statistical analyses will be performed in conjunction with the consultant biostatistician([name]). The proposed sample size of 20 subjects for the Phase II expansion cohort was determined to detect, with an 80% power at a 5% type-1 error rate, a change of 15.9 points on the primary endpoint (ie. SNOT-22 score) between baseline and 4 weeks. This calculation was based on two assumptions. The first is a target effect size of 15.9 which represents a conservative value derived from the established MCID for the SNOT-22 of 8.9[65] and the LSM change in SNOT-22 of 27.7 derived from our previous trial of oral Verapamil(Section R.4.d)[19]. The second is an anticipated standard deviation of 24 which is calculated from the standard deviations of 30 both at the baseline and 8 week time point observed in our oral Verapamil trial and an r2 of 50% between the two time points. With a significance level of 0.05, a standard deviation of 24, and 80% power, a sample size of 20 would be needed to detect a difference of 15.9. Analysis of efficacy will be based on an intention-to-treat population that will include all enrolled patients. A mixed-effect model with repeated measures approach will be used to independently analyze the change in the SNOT-22, VAS, and LKS. An intraclass correlation coefficient (ICC) will be calculated to assess inter-rater agreement with respect to the LKS scores. Descriptive statistics will be used for demographics, baseline characteristics, and safety variables. Linear regression models will be fitted to examine the interaction effect between baseline characteristics, whole mucus and exosomal P-gp concentrations, mucus and irrigant cytokine concentrations, and treatment on change in SNOT-22 while adjusting for the baseline SNOT-22 score. Statistical analyses will be performed using the statistical software SAS (SAS Institute Inc., Cary, NC)

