10.3 ANALYSIS DATASETS

Phase Ib:

All patients in the Phase Ib arm will be part of the Safety Analysis Dataset

Phase II:

The Phase II participants will be included in an intention-to-treat dataset and a safety analysis dataset.

Participants who used at least 80% of the topical verapamil during the one month period will be considered an evaluable dataset.

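### Phase II early exits are replaced with no day-28 follow-up, so the promised intention-to-treat result may in effect become a completer result

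*Combined protocol and SAP*

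**What the plan says.** Section 5.4.1 (Arm 2) gives three ways out of Phase II:

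- Adherence: "The PI will terminate a participant if they miss more than 2 doses of topical Verapamil in a week".
- Safety: "The PI will terminate a Phase II study participant if they present with any clinical adverse event (AE) or other medical complication", qualified by the PI's judgement that staying in would not serve the participant.
- The participant's own request.

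Sections 5.4.1 and 5.4.2 both add: "Any withdrawn participant will be replaced with a new enrollment". Follow-up after leaving is described only for people who leave "due to an adverse event will be followed for up to 1 year to monitor for additional safety data". Section 7.3.5 adds an exit assessment: "In the event of an early termination participants will be asked to perform all the procedures for the final visit". For Phase II that includes a SNOT-22, taken when the person leaves.

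On analysis, Section 10.1 states: "Analysis of efficacy will be based on an intention-to-treat population that will include all enrolled patients", and names a mixed model with repeated measures. Section 10.2 frames the hypothesis as baseline against week 4. Section 10.4.2 tests the primary endpoint with a Student's t-test or a Mann-Whitney U test. Section 10.3 defines an evaluable set as "Participants who used at least 80% of the topical verapamil during the one month period". Section 4.1 fixes Phase II at 20 patients.

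**The concern.** An intention-to-treat promise has content only if the people who leave still supply the outcome, or if the plan says what stands in for it. Here neither is provided. There is no week-4 efficacy visit after early exit, no missing-data rule, no rule for the exit SNOT-22, and no statement that a replaced participant and the replacement both count.

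Missing doses, having adverse events and asking to leave are plausibly linked to poor tolerability or little benefit. If such people are swapped for new ones until 20 have week-4 scores, the 20 are a selected group. Section 10.6.1 confirms that there is no randomization or blinding, so no comparator would carry the same selection and cancel it. The estimate at stake is the mean SNOT-22 change, which is the Phase II primary endpoint.

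**Working it through.** **1. The plan's own figure.** Inputs from Sections 10.1 and 10.5: difference 15.9, SD of change 24, significance level 0.05 (taken as two-sided), power 80%. For a paired t-test with n = 20, the noncentrality is 15.9/24 × √20 = 2.96 and the power is 80.2%. With n = 19 it is 78.0%. The stated 20 reproduces. The point is about who is analysed, not about that calculation.

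**2. Who reaches the week-4 test.** A paired comparison of baseline with week 4 needs both scores. Someone who exits early has a baseline score, perhaps a week-1 score, and an exit score at an unscheduled time. Under Section 10.4.2 that person contributes nothing unless the exit score is treated as week 4, which no section says. Under the Section 10.1 mixed model, the baseline and week-1 scores still contribute.

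**3. Size of the selection effect.** Let d be the fraction removed, m_s the mean improvement in stayers and m_l that in leavers. The mean over everyone enrolled is (1 − d)·m_s + d·m_l, so the completer mean overstates it by d·(m_s − m_l). The documents give neither d nor m_l. Assume d = 10–20% and m_s = 15.9.

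| Leavers' mean improvement | All-enrolled mean, d = 10% / 20% | Overstatement, d = 10% / 20% |
|---|---|---|
| 15.9 (same as stayers) | 15.9 / 15.9 | 0 / 0 |
| 7.95 (half) | 15.1 / 14.3 | 0.8 / 1.6 |
| 0 (none) | 14.3 / 12.7 | 1.6 / 3.2 |

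Reaching 20 completers would mean enrolling 20/0.9 = 22.2, so 23, or 20/0.8 = 25.

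**4. Would the mixed model cure it?** This was simulated with no true change and enrolment until there were 20 completers, using 4,000 runs per setting. The assumptions were SD 24, a correlation of 0.7 between week-1 and week-4 change, and exit correlated 0.5 with poor response. Every leaver was assumed to supply a week-1 score. The nominal chance of a significant result in the favourable direction is 2.5%.

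| Exit depends on | Completer bias, 10% / 20% removed | Chance of significant benefit under the completer t-test | Mixed-model-type bias |
|---|---|---|---|
| Week-1 response (observed) | +1.6 / +2.8 | 5% / 7% | +0.1 / 0.0 |
| Week-4 response (unseen) | +2.4 / +4.2 | 6% / 11% | +1.4 / +2.4 |

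When exit was unrelated to response, neither estimate was biased beyond simulation error.

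**5. The two adherence rules.** Twice daily for 28 days is 56 doses.

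- Someone who never breaches the weekly rule misses at most 2 × 4 = 8, so takes at least 48/56 = 85.7% and is always evaluable.
- Someone who misses 3 doses in one week and none otherwise takes 53/56 = 94.6%. That meets the 80% criterion, yet the person is to be terminated.
- Someone who misses 4 doses in each of weeks 2–4, found only at the final visit, takes 44/56 = 78.6%. That person has a week-4 SNOT-22 and is not evaluable, so the sets can differ.

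**The case against.** A reader might infer that the plan simply turns intention-to-treat into a completer analysis, that benefit will be overstated, and that the 80% set is redundant. The documents do not support that much.

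- **Nothing removes leavers from the intention-to-treat set.** Section 10.1 includes everyone enrolled, its mixed model uses their earlier visits, and Section 7.3.5 obtains a SNOT-22 at exit. This stands. The loss occurs under the Section 10.4.2 test, and the plan does not say which of the two methods is primary.
- **The missed-dose rule may cost few week-4 scores.** Sections 6.1.10 and 10.4.5 have staff check the dosing calendar at visits, and Phase II follow-up visits are only at weeks 1 and 4. Lapses in weeks 2–4 would usually surface when the final SNOT-22 is being taken. This stands for late lapses. It does not cover lapses found at week 1, adverse-event terminations or withdrawals.
- **Replacement is written for withdrawn participants.** Section 5.4.2 distinguishes withdrawing from being terminated. Including those terminated is the natural reading under that section's title, but it is not explicit.
- **Direction and size are assumed.** With no removal rate and no outcomes for leavers, zero bias is possible. This stands.
- **The effect is modest.** Even 3.2 points is below the standard error of the mean change (24/√20 = 5.4) and below the MCID of 8.9 in Section 10.1. That is fair, and it limits the severity. However, random error is reflected in the confidence interval, whereas a shift of this kind is not.
- **The 80% set still has a role.** As the last example in the working shows, it can differ from the set with week-4 data when late lapses are found only at the final visit.

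**Conclusion.** The concern holds in a limited form. As written, the plan leaves the promised all-enrolled estimate open to selection, because early leavers have no planned day-28 efficacy assessment, their exit score has no stated use, and their standing next to their replacements is undefined. If the Section 10.4.2 t-test is used, the primary result may be a completer result in all but name. Overstatement is the likely direction but not a certain one. It is 0 to 3.2 points under an assumed 10–20% removal and stayers improving by 15.9, with the upper end requiring no benefit at all in leavers. The mixed model largely removes the bias if exit follows observed week-1 scores, and only reduces it if exit follows later, unseen response.

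Separately, the weekly missed-dose rule and the 80% evaluable rule are not aligned. This should be fixed, but it does not invalidate the design or the sample size of 20.

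**What to change.** - **Sections 5.4 and 7.3.5:** separate stopping study drug from leaving follow-up. Collect SNOT-22, VAS and LKS at day 28 on every dosed participant who has not withdrawn consent. State whether replacement applies to terminated as well as withdrawn participants.
- **Sections 10.1 and 10.3:** state that the primary set keeps replaced participants as well as their replacements, so that replacements add to the number analysed.
- **Sections 10.1 and 10.4.2:** make the mixed model, using all available visits, the primary analysis in place of the t-test. Say how an exit SNOT-22 enters it. Add a sensitivity analysis assuming no change from baseline for anyone without day-28 data.
- **Reporting:** give the number replaced and the reasons.
- **Adherence rules:** the sponsor should reconcile the weekly missed-dose rule with the 80% evaluable rule. This review takes no view on which threshold is right.

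The cost is wording plus a few extra day-28 assessments: about 3 to 5 people if 23 to 25 are enrolled to obtain 20 completers. The estimate may be slightly less favourable.

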5.4.2 HANDLING OF PARTICIPANT WITHDRAWALS OR TERMINATION

Patients that withdraw or are terminated from either arm of the study due to an adverse event will be followed for up to 1 year to monitor for additional safety data.

Phase 1B: Any withdrawn participants will be replaced to maintain 3 patient cohorts.. Their reason for withdrawal will be noted.

Phase 2: Any withdrawn participant will be replaced with a new enrollment.

5.5 PREMATURE TERMINATION OR SUSPENSION OF STUDY

This study may be temporarily suspended or prematurely terminated if there is sufficient reasonable cause. Written notification, documenting the reason for study suspension or termination, will be provided by the suspending or terminating party to the investigator. If the study is prematurely terminated or suspended, the PI will promptly inform the IRB and will provide the reason(s) for the termination or suspension.

Circumstances that may warrant termination or suspension include, but are not limited to:

- Determination of unexpected, significant, or unacceptable risk to participants including a greater than 20% AE rate
- Demonstration of efficacy that would warrant stopping
- Insufficient compliance to protocol requirements
- Data that are not sufficiently complete and/or evaluable
- Determination of futility

Study may resume once concerns about safety, protocol compliance, data quality are addressed and satisfy the sponsor, IRB and/or FDA.

6 STUDY AGENT

6.1 STUDY AGENT(S) AND CONTROL DESCRIPTION

6.1.1 ACQUISITION

The Verapamil HCl irrigations will be acquired from the MEEI Pharmacy. [name] will be in charge of the prepareation of each dose.

6.1.2 FORMULATION, APPEARANCE, PACKAGING, AND LABELING

Phase Ib

Verapamil solution for injection, supplied in vials, will be utilized for this phase of the trial. Verapamil solution for injection in vials is commercially available through the Pharmacy's wholesaler (Cardinal Health). Depending on specific product availability from the wholesaler, one of the following verapamil solution for injection in vial will be used:

- Verapamil 10mg/4mL vial (NDC 00409-1144-02, manufacturer = Hospira) **This is the preferred product if available in sufficient quantity from the wholesaler.**
- Verapamil 5mg/2mL vial (NDC 00409-1144-05, manufacturer = Hospira)
- Verapamil 5mg/2mL vial (NDC 51754-0203-02, manufacturer = Exela Pharma Sciences)

Verapamil is not available for use via the nasal irrigation route and must be formulated in Neil Med Sinus Rinse to be utilized as an irrigation.

Neil Med Sinus Rinse is commercially available through the Pharmacy's wholesaler (Cardinal Health). The Neil Med Sinus Rinse starter kit (with bottle and 5 packets, NDC 05928-0003-08, manufacturer = NeilMed Products, Inc.) and Neil Med Sinus Rinse refill packets (NDC 05928-0002-00, manufacturer = Neil Med Products, Inc.) will be used.

Please see attached package inserts (included in appendix) for more information.

6.1.3 PRODUCT STORAGE AND STABILITY

Verapamil in its commercially available form (vials or syringes) is stored at controlled room temperature (15-30 degrees C) and protected from light in its original container. Verapamil commercially available vials and syringes are single use products; if any extra medication remains in the original container after preparing the patient-specific dose it will be discarded. Verapamil will be stored in the Pharmacy in a limited access area and segregated from standard pharmacy stock; it will be specifically allocated as a supply for this trial. When patient-specific verapamil doses are prepared, the beyond-use dating will be 9 days at refrigerated temperature (2-8 degrees C)

Neil Med Sinus Rinse in its commercially available form is stored at controlled room temperature (15-30 degrees C). Neil Med packets are for single use only. Neil Med Sinus Rinse will be stored in the Pharmacy in a limited access area and segregated from standard pharmacy stock; it will be specifically allocated as a supply for this trial. When patient-specific verapamil doses are combined with Neil Med Sinus Rinse, the final product should be used immediately..

6.1.4 PREPARATION

Phase Ib

Patient-specific verapamil doses will be drawn up from the commercially available verapamil vials utilizing aseptic technique in an ISO Class 5 biological safety cabinet in the Pharmacy. At the time of use, patients will prepare the Neil Med sinus rinse from the packet according to the manufacturer's directions for preparation. The patient will transfer the verapamil from the Pharmacy-supplied syringe into the bottle containing the Neil Med sinus rinse and use immediately for nasal irrigation.

Phase II

Patient-specific verapamil doses will be provided in commercially available verapamil syringes. At the time of use, patients will prepare the Neil Med sinus rinse from the packet according to the manufacturer's directions for preparation. The patient will transfer the verapamil from the Pharmacy-supplied syringe into the bottle containing the Neil Med sinus rinse and use immediately for nasal irrigation..

6.1.5 DOSING AND ADMINISTRATION

Phase Ib:

Phase Ib participants will receive dosing according to the included escalation schedule. Dosing will go from an initial 0.3-3.6mg total residual dose of Verapamil HCl. Phase II Participants will receive the MAD determined by Phase Ib. Participants will administer the irrigation BID. A video demonstration on proper administration of the irrigation will be shown at the initial study visit.

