BP	Blood Pressure				
CRF					
	Case Report Form Chronic Rhinosinusitis				
CRS					
DLT	Dose Limiting Toxicity				
DSMB	Data and Safety Monitoring Board				
EKG	Electrocardiogram				
ELISA	Enzyme Linked Immunosorbent Assay				
FDA	Food and Drug Administration				
GAPDH	Glyceraldehyde-3-Phosphate Dehydrogenase				
GCP	Good Clinical Practice				
HCl	Hydrochloride				
IHC	Immunohistochemistry				
IL	Interleukin				
IN	Intranasal				
IND	Investigational New Drug				
IRB	Institutional Review Board				
ICC	Intraclass Correlation Coefficient				
IŢ	Intermediate Toxicity				
LMK	Lund-Mackay				
LKS	Lund-Kennedy Score				
LSM	Least Squares Mean				
MAD	Maximal Administered Dose				
MAP	Mean Arterial Pressure				
MCID	Minimally Clinically Important Difference				
MEEI	Massachusetts Eye and Ear Infirmary				
MTD	Maximal Tolerated Dose				
PBS	Phosphate Buffered Saline				
PCFD	Partition Coefficient of the Free Drug				
P-gp	P-glycoprotein P-glycoprotein				
PI	Principle Investigator				
PVA	Polyvinyl Alcohol Sponge				
SA	Specific Aims				
SNOT-22	Sinonasal Outcomes Test (22-item)				
sNP	Without Nasal Polyps				
SEB	Staphylococcal aureus enterotoxin B				
TEM	Transmission Electron Microscopy				
Th2	Type 2 Helper T-cell				
TID	Three Times a Day				
TSLP	Thymic Stromal Lymphoprotein				
UCF	Ultracentrifugation				
wNP	With Nasal Polyps				
VAS	Visual Analog Scale				
	ž				
Zos	Zosuquidar Trihydrochloride				

STATEMENT OF COMPLIANCE

This trial will be conducted in accordance with the ICH E6, the Code of Federal Regulations on the Protection of Human Subjects (45 CFR Part 46), and the <NIH IC> Terms of Award. The Principal Investigator will assure that no deviation from, or changes to the protocol will take place without prior agreement from the sponsor and documented approval from the Institutional Review Board (IRB), except where necessary to eliminate an immediate hazard(s) to the trial participants. All personnel involved in the conduct of this study have completed Human Subjects Protection Training.

I agree to ensure that all staff members involved in the conduct of this study are informed about their obligations in meeting the above commitments.

Principal Investigator: _		
	Print/Type Name	
Signed:		_ Date:

PROTOCOL SUMMARY

Title: Phase Ib/II Clinical Trial of Topical Verapamil HCl for Chronic Rhinosinusitis with Nasal

Précis: Phase Ib will be an accelerated titration, intrapatient dose escalation cohort, with double-

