> dose step design. Participants will administer each dose Verapamil HCl dose intranasally BID. Weekly visits will occur for side-effect and escalation evaluations. Phase II will be an open label trial of 20 participants. The MTD determined in Phase Ib will be administered BID for 4 weeks.

Participants will be seen at baseline, 1 week, and 4 week for efficacy and side-effect

evaluations.

Objectives: Primary Objectives:

> -Perform a Phase IB trial of topical intranasal Verapamil HCl BID to determine the Maximal Tolerated Dose(MTD) using an accelerated titration design with intra-patient dose escalation. -Perform a Phase II trial of topical intranasal Verapamil HCl BID based on the Phase I MTD to determine safety and efficacy using both subjective and objective outcome measures of CRS. Secondary Objective:

-Determine whether mucus derived exosomal P-gp can be used as a non-invasive biomarker of CRS by correlating it with baseline symptoms of CRSwNP and treatment response to topical

Verapamil HCl at the MTD. **Endpoint**

Primary Endpoints:

Phase Ib: Defining the Maximal Tolerated Dose(MTD) of topical Verapamil HCl. DLT will be defined as a development of 2nd or 3rd degree heart block as measured by an EKG.

Phase II: determining the efficacy of topical Verapamil HCl at the MTD for subjective symptoms

of CRSwNP using the validated SNOT-22.

Secondary Endpoints:

Phase Ib: Intermediate toxicity will be defined as: a heart rate of <50, an asymptomatic BP reduction >30% from baseline or SBP <90mmHg, an asymptomatic AMP reduction >30% from baseline or MAP<55, an asymptomatic DBP reduction >30% from baseline, and a Meltzer Compliance Grade >4.

Phase II: to determine the efficacy of Verapamil HCl at the MTD as measured by a subjective 10cm visual analog scale(VAS), Meltzer topical irrigation satisfaction and compliance scores, and the validated Lund-Kennedy nasal endoscopy score(LKS).

Population: 20-40 MEE Sinus Center patients over the age of 18 who present with chronic

rhinosinusitis with polyps.

Phase: IB/II
Number of 1

Sites enrolling participants:

Description Verapamil HCl 0.3mg-3.6mg final dose BID in buffered normal saline as a nasal

of Study irrigation.

Agent:

[figure not shown]
Study December 2016 – December 2018

Duration:

[figure not shown]
Participant 1 month

Duration:

SCHEMATIC OF STUDY DESIGN

Legend				
IC	Informed Consent			
IF	Intake Form			
PT	Pregnancy Test			
SNOT-22	Sino-Nasal Outcome Test			
VAS	Visual Analogue Scale			

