4 STUDY DESIGN AND ENDPOINTS

4.1 DESCRIPTION OF THE STUDY DESIGN

ARM 1: Phase 1B

The phase IB study will consist of an accelerated titration, intrapatient dose escalation cohort, with double-dose step design. The initial single patient cohort will begin by taking 0.3mg (10mg of Verapamil in 240mL of buffered normal saline yielding an established 3% residual nasal dose) as a nasal irrigation BID for 1 week. The first dose f

each escalation will be administered in a 10th or 11th floor MEE clinic withhemodynamic monitoring. A medically trained member of the study staff with monitor the patient for one hour. Patients will be instructed on the how to properly perform the irrigation using a pre-recorded video demonstration. If no first-course dose limiting toxicity (DLT, defined by the development of 2nd or 3rd degree heart block) is noted then patients will continue taking the current Verapamil rinse dose BID for 1 week. Dose escalation will occur weekly in the absence of a single, any course, DLT or a second, any course, intermediate toxicity(IT, defined by a heart rate of <50, an asymptomatic BP reduction >30% from baseline or systolic BP <90mmHg, an asymptomatic MAP reduction >30% from baseline or MAP<55, an asymptomatic diastolic BP reduction >30% from baseline, and a Meltzer Compliance Grade >4[60]). Each escalation will be a doubling of the dose from 0.3-2.4mg. At that point that dose will escalate in 0.6mg residual intervals for the rest of the trial up to a maximum of 3.6mg total residual dose. These doses were derived from the pharmacokinetic analysis of our oral Verapamil trial results. If a single, any course, DLT or second, any course, IT occurs, two additional patients will be recruited at that identified dose and Phase IB will revert to a standard 3+3 design. If any patient un-enrolls while the dose escalation is still occurring, they will be replaced to maintain 3 patient cohorts. The maximal administered dose(MAD) will be considered that at which at least 2 DLTs or 4 ITs occur and the MTD will then be assigned to the immediate preceeding dose.

At each weekly visit, the patients nasal endoscopy will be recorded for LKS grading, and they will be administered symptom, side-effect, and tolerability questionnaires. Pre-dosing mucus and post-dosing irrigant samples will also be atraumatically collected from the nasal cavity for use in exosomal biomarker sampling.

ARM 2: Phase 2

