The Phase II study will be an open label safety and efficacy expansion cohort using the MTD determined in the Phase IB arm. A total of 20 patients will be administered the MTD of topical Verapamil HCl in a 240mL buffered normal nasal rinse for 4 weeks BID. This sample size was calculated based on a power analysis derived from the results of our oral Verapamil trial. The first dose will be administered in in a 10th or 11th floor MEE clinic withhemodynamic monitoring. A medically trained member of the study staff with monitor the patient for one hour. Patients will be instructed on the how to properly perform the irrigation using a pre-recorded video demonstration. If no first-course DLT occurs then patients will continue taking the topical Verapamil dose BID. Patients will then return for follow-up visits at 1 week and 4 weeks. Subjective and objective outcome measures will be collected at each visit.

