7.3.4 FINAL STUDY VISIT

Phase 1B:

Participants will have their final study visit when they experience DLT and are removed from the study, choose to end their participation, or achive the maximal administered dose. The reason for the drop-out will be noted in the participant file. Participants will be asked to fil out a SNOT-22, VAS, Satisfaction scale, and Compliance scale and will be evaluated for side-effects. An endoscopy will be recorded and scored. A mucus sample will be collected from the nasal cavity with a small sponge. Participants will receive their compensation at the end of the final visit.

Phase 2:

During the Week 4 visit participants will be asked to fill out a SNOT-22, VAS, Satisfaction scale, and Compliance scale. Adherence to the treatment regimen will be evaluated. Participants will be evaluated for side-effects. An endoscopy will be recorded and scored. A mucus sample will be collected from the nasal cavity with a small sponge. Participants will receive their compensation at the end of the final visit.

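### Section 6.1.5 gives Phase II the MAD, the dose that met the toxicity criterion; the other available sections that name a Phase II dose give the MTD, one level lower

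*Combined protocol and SAP*

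**What the plan says.** Section 4.1 (Arm 1) defines both terms. For the MAD: "The maximal administered dose(MAD) will be considered that at which at least 2 DLTs or 4 ITs occur". For the MTD: "the MTD will then be assigned to the immediate preceeding dose". They are therefore adjacent levels of the escalation ladder, and the List of Abbreviations gives them separate entries, "Maximal Administered Dose" and "Maximal Tolerated Dose".

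On the Phase II dose, section 6.1.5 says: "Phase II Participants will receive the MAD determined by Phase Ib".

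Section 4.1 (Arm 2) says: "A total of 20 patients will be administered the MTD of topical Verapamil HCl". The Protocol Summary says: "The MTD determined in Phase Ib will be administered BID for 4 weeks". The Phase II objective in section 3 and the Phase II endpoints in sections 4.2.1 and 4.2.2 also refer to the MTD. Section 6.1.7 says only that Phase Ib determines the Phase II dose, without naming either term. Section 6.1.8 rules out any change of the Phase II dose during the 4 weeks.

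**The concern.** By the protocol's own definitions, 6.1.5 sends Phase II participants to the level that met the toxicity criterion, and the remaining sections send them one level lower. Both cannot be followed.

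Two things would be at stake if 6.1.5 were followed:

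- **Safety.** Verapamil is cardioactive, and the DLT is second- or third-degree heart block. Phase Ib participants escalate weekly, while Phase II lasts 4 weeks, so exposure at the MAD could last longer than the exposure that showed the toxicity. Because 6.1.8 allows no dose change, a participant given the wrong level could be stopped but not stepped down to the MTD.
- **Interpretation.** The Phase II objective and endpoints concern safety and efficacy at the MTD. A cohort treated at the MAD would not answer that question.

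**Working it through.** **Step 1. Compare the sections that bear on the Phase II dose.**

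| Place | Phase II dose |
|---|---|
| Protocol Summary | MTD |
| Section 3 | MTD |
| Section 4.1, Arm 2 | MTD |
| Section 4.2.1 | MTD |
| Section 4.2.2 | MTD |
| Section 6.1.5 | MAD |
| Section 6.1.7 | set by Phase Ib, term not named |

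In the text available, only 6.1.5 assigns the MAD to Phase II. Section 6.1.7, the nearest place where a correction could stand, does not supply one.

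**Step 2. Test whether the terms could be synonyms.** Section 4.1 makes them different levels by construction. The only later use of the full term is in section 7.3.4, where a Phase Ib participant's final visit can be triggered by several events, the last being "or achive the maximal administered dose". That wording neither redefines the term nor names a Phase II dose.

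**Step 3. Size of the difference.** Inputs:

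- Residual dose ladder (6.1.7): 0.3, 0.6, 1.2, 2.4, 3.0, 3.6 mg.
- Retention (4.1): 10 mg in the bottle leaves 0.3 mg, so bottle content = residual dose / 0.03.
- Phase II schedule (4.1): twice daily for 4 weeks, or 2 × 28 = 56 irrigations.

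For each possible MAD, the MTD is the level below it. Ratio = MAD / MTD; excess = MAD − MTD; bottle excess = excess / 0.03; daily excess = 2 × excess.

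| MAD (mg) | MTD (mg) | Ratio | Excess per irrigation (mg residual) | Excess in bottle (mg) | Excess per day (mg residual) |
|---|---|---|---|---|---|
| 0.6 | 0.3 | 2.0 | 0.3 | 10 | 0.6 |
| 1.2 | 0.6 | 2.0 | 0.6 | 20 | 1.2 |
| 2.4 | 1.2 | 2.0 | 1.2 | 40 | 2.4 |
| 3.0 | 2.4 | 1.25 | 0.6 | 20 | 1.2 |
| 3.6 | 3.0 | 1.2 | 0.6 | 20 | 1.2 |

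Over a completed course the cumulative excess runs from 56 × 0.3 = 16.8 mg to 56 × 1.2 = 67.2 mg residual. These are sums over 56 irrigations and should not be set beside single-dose figures.

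**Step 4. Would another part of the plan catch the error?** Two steps precede Phase II dosing and could in principle do so: DSMB review during Phase Ib (section 9) and the study prescription form (section 6.2). Neither is described as a check of the Phase II dose level. The exclusion criteria (5.2) and the EKGs before the first dose (2.3.1, 7.3.2) reduce cardiac risk but do not check the level. The remaining safeguards act once dosing has begun:

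- the monitored first irrigation, with the rest of the drug withheld if the EKG is judged unsafe (4.1, 7.3.2);
- the week 1 EKG (10.4.7.1);
- termination by the investigator for an adverse event that makes continuing against the participant's interest (5.4.1);
- DSMB review at 10 Phase II participants (section 9);
- the halting rules (8.5, 10.4.7.1).

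**The case against.** The strongest reply is that the intended dose is not in doubt. Five places give the MTD, and one of them, section 4.1 (Arm 2), is itself a direct dosing instruction. Harm requires both that a MAD is reached above 0.3 mg and that one sentence is preferred to all the others. This stands, and it is why the point is called a probable slip. It does not make the sentence in the dosing section correct.

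The clinical scale also deserves mention. Section 2.1 puts the twice-daily intranasal dose equivalent to 80 mg oral three times daily at 16.8 to 72.75 mg, and reports no significant side effects in the sponsor's oral trial. If residual dose is comparable with that intranasal dose, which is an assumption, the largest excess is 1.2 / 16.8 = 7% of the lower bound and the top of the ladder is 3.6 / 16.8 = 21%. Nor need a MAD reflect heart block: 4 ITs suffice, and these include asymptomatic blood pressure falls and a Meltzer Compliance Grade above 4. Both points temper the 2.0-fold ratio. However, reaching a MAD would itself be evidence of poor tolerance at that level.

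Section 7.3.4 might use the term loosely, for the highest dose actually given. That is possible, but 6.1.5 uses the abbreviation, which section 4.1 defines expressly.

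Finally, the DSMB charter, the prescription form or other documents not available here might state the dose or contain a check. That cannot be excluded. It would not remove the conflict within the protocol.

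**Conclusion.** The concern holds and must be fixed. Section 6.1.5 contradicts section 4.1 (Arm 2), the Protocol Summary, the Phase II objective and the Phase II endpoints. Followed as written, it gives a dose 100% above the MTD if the MAD is 0.6, 1.2 or 2.4 mg, 25% above if it is 3.0 mg, and 20% above if it is 3.6 mg.

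The size depends on a MAD being reached above 0.3 mg and on 6.1.5 being followed; the documents give no basis for a probability of either. The contradiction itself depends on neither, and rests only on the definitions in section 4.1. The finding is limited to the text available for review.

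**What to change.** - **Section 6.1.5:** replace MAD with MTD in the Phase II sentence.
- **Section 6.1.7:** change the last line to state that the Phase II dose will be the MTD determined by Phase Ib.
- **Section 4.1, useful in the same amendment:** add one sentence saying what happens if no level up to 3.6 mg meets the MAD criterion, or if 0.3 mg does. The MTD is defined only relative to a MAD, so in either case the corrected 6.1.5 would still leave Phase II without a defined dose. This is a separate gap, and the finding does not rest on it.

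The cost is a wording change by protocol amendment, with no added patients, visits or analyses.
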